# 8.5.2 Secondary Efficacy Endpoints

Secondary efficacy endpoints include the disease control rate, duration of response, progression-free survival (PFS), and overall survival (OS).

Duration of response is defined as the duration that subjects who have responded to combination therapy remain without disease progression.

Disease control rate is defined as the percentage of patients who have achieved complete response, partial response and stable disease.

Progression-free survival (PFS) is defined as time from registration to progression or death due to any cause. Progression is defined as radiologic progression of disease by RECIST v1.1 criteria.

Overall survival (OS) is defined as the time from registration until death from any cause,

# 8.5.3 Exploratory Analysis

Correlative endpoints include the following:

• To examine the tumor-immune microenvironment prior to and following OBP-301 and pembrolizumab therapy as assessed by bulk RNA sequencing and single-cell RNA sequencing.

• To examine and characterize the immune infiltrate by multi-parameter flow cytometry.

# 8.5.4 Methods for Analysis

Endpoints involving response rates will be analysed by tabulating the response rates along with 95% confidence interval and number of patients with data for each time point that the endpoint is collected. Waterfall plots for tumor response (CR, PR, and ORR) will be provided.

Endpoints involving time to event or time to response will be analysed using survival analysis, including Kaplan-Meier plots. Median survival time with 95% confidence interval, 25th-75th percentiles will be provided.

Exploratory subgroup analyses for tumor response will be defined in the statistical analysis plan (SAP).

# 8.6 Correlative Study

All patients undergoing treatment with OBP-301 will have tissue biopsies along with correlative blood samples. Tissue biopsies will be performed with every injection of OBP-301. Correlative blood samples will be taken before the start of study treatment, during treatment and post-treatment as described in the section of study schedule. Correlative studies are focused on a detailed and comprehensive evaluation of the tumor immune microenvironment as it

relates to induction of the anti-tumor immune response. Specific procurement and shipping instructions will be provided to participating sites upon study activation. Our specific correlative studies include the following:

# A) To examine the tumor-immune microenvironment prior to and following OBP-301 and pembrolizumab therapy as assessed by bulk RNA sequencing and single-cell RNA sequencing.

The focus in this application is to perform detailed cellular characterization of gastric and GEJ tumors and their microbial environment towards better understanding of the factors that shape the response to immunotherapies and mechanism of resistance. To address this, we propose to perform single cell expression analysis and microbiome profiling of tissue samples collected from patients with esophageal/gastric tumors.

We hypothesize that surveying the immune infiltration in the context of immunotherapy and OBP-301 will provide important biomarker for response to treatment. To address this, we propose the following studies: Sub-aim (1) Identify and quantify the cellular composition of tumor and adjacent normal tissues from esophageal and gastric cancer patients. Single cell profiling will be performed on each sample collected from patient recruited to the study at Weill Cornell and microbiome detection by whole genome sequencing at baseline (prior to treatment). Sub-aim (2) Generate a patient-specific profile of tumor microenvironment. In this aim the data collected in Aim1 will be analyzed to identify the cell types that are present in each patient at onset of treatment and how cellular composition changes in response to treatment. By computational approaches we will cluster the cells from each sample by their expression profile to distinct groups representing specific cell types (e.g. mucosa layer, lymphocytes, CD45+, squamous epithelium). Similarly, we will identify various immune cells such as CD8+ and CD4+, effector T cells, Treg and others immune subtypes and correlate with microbiome composition. In addition, we will survey levels of PD-1, PD-L1/2, CD28 and other known marker of checkpoint inhibitor response. Sub-aim (3) Longitudinal profiling of patients before and after immunotherapy + OBP-301 to identify possible biomarkers for response and mechanism of resistance. In this aim we will summarize the results from all patient data to assess what are the consistent changes observed in cellular composition in response to immunotherapy and we will investigate how these changes impact response to treatment.

# B) To examine the T-cell response in responding and resistant individuals by TCR-sequencing on pre- and post- treatment tumor biopsies.

The primary aim of this proposal is to overcome inherent resistance to immunotherapy in foregut tumors with the addition of a replication-selective oncolytic virus. This project will be focused on analyzing the immune landscape of individual tumors from tumor biopsies taken at baseline and on therapy. We will analyze changes associated with relapse and differences between refractory and sensitive patients. Our proposed analysis will take as input somatic mutations, raw WES reads, and raw RNA-Seq reads. In addition we will perform direct TCR-seq. We will run our existing pipeline for neoepitope prediction, expression, and TCRseq analysis. The output will be an immune landscape per tumor, including (1) mutation burden and high-affinity predicted neoepitopes, (2) checkpoint expression and immune composition, and (3) TCR-seq estimated profiles together with infiltration and diversity values. Comprehensive analysis of entire cohorts will reveal tumor type specific patterns such as correlation specific mutations and immune infiltration and repertoires as well as overrepresentation of specific T cell clones and signature of neoepitope burden.

For sub-aim (1) we will perform whole exome sequencing via the Englander Institute pipeline and apply state of the art neoantigen discovery tools. We will validate high affinity neoantigens using in vitro assay involving synthetic peptides and a patient's own T cell where we measure T cell clonal expansion using TCR-seq from Archer DX (test already available in Weill Cornell's genomics core). We will explore evolution of neoantigen in relapse biopsies. For subaim (2), we will perform RNAseq and TCR-seq using ArcherDX, then deconvolute using Cibersort and another in-house approach that takes into account lineage relationship between reference cell types. As needed we will perform single cell RNAseq to obtain orthogonal validation data. We will correlate immune cell type abundance and TCR repertoires with clinical outcomes. In sub-aim (3) we will develop an immunoscore that uses features defined by immune landscape analysis to build a predictive model of who will respond to immunotherapy. We will pre-train the model using genome profiling results from two recent studies of melanoma datasets treated with anti CTLA4 antibodies, then fine tune via transfer learning using the data from the trials. A variety of machine learning models such as logistic regression, random forest and deep learning will be tested and evaluated using cross-validation. We note that we have extensive experience building such models and that machine learning models we built have shown clinical value. We will determine how the immunoscore correlates with clinical outcome such as progression free survival (PFS) in prospective future trials. We will evaluate the immunoediting patterns of these cohorts, that is, identify variants whose presence is inversely correlated with T cell infiltration. The results will be presented as heatmaps and tables.

#### C) To examine and characterize the immune infiltrate by multi-parameter flowcytometry.

In this application, innovative multi-parameter flow cytometry will be utilized that will provide single-cell high resolution of immune cell suppression or activation. Our collaborator, [name] has developed technologies to cryopreserve viable immune cells from primary human tissues and tumor biopsies or resections for side-by-side analyses of immune cells from multiple patients, thus reducing sample variation and allowing direct single-cell comparisons of cytokine production. This powerful approach will be utilized to characterize tumor immune cell infiltrates at baseline, following the induction of combination therapy and at the time of resection. This will be one of the first longitudinal analyses of tumor immune cell infiltrates by multi-parameter flow cytometry following immunotherapy.

#### 8.7 Safety Analyses

# 8.7.1 Safety Endpoints

The primary safety endpoint is to examine the safety of multiple OBP-301 intratumoral injections in combination with pembrolizumab in advanced esophagogastric cancer.

#### 8.7.2 Summary of Adverse Events

All adverse events, as defined in Section 7, will be recorded for each patient. Adverse events will be tabulated for all patients by: first occurrence of each adverse event, maximum severity, and relationship to treatment. Treatment-related AEs and serious AEs will be tabulated separately, by first occurrence, maximum severity, and strongest relationship to treatment. A listing of all AEs will also be included, per patient, including onset/resolution date, severity, relationship to study treatment, and action regarding IP. A listing of all discontinuations, injection delays, and deaths due to adverse events in the study will be included.

#### 8.7.3 Summary of Laboratory Assessments

Summary statistics will be presented for all blood chemistry, hematology, coagulation, and urinalysis results by study visit, where data are collected.

In addition, all laboratory values will be flagged as low (L1, L2, L3, or L4), high (H1, H2, H3, or H4) or normal (N) based on the investigational site laboratory normal range and/or the NCI toxicity criteria. Shifts in assessments from baseline to all post-baseline visits will be presented (shift tables).

#### 8.7.4 Summary of Special Laboratory Assessments

Summary statistics and shift tables will be presented for all special laboratories results including cytokines, and immune cell phenotypes by study visit, where data are collected.

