# 6.1 Schedule of Events

	Screeni	ng Phase						Тı	reatmen	t Phase					
Treatment Encounter	Part 1	Part 2	Baseline	1	2	3	4	5	6	7	8	9	10	11	12
Scheduling Window	(-28 to -1)	(-14 to -1)	Day 0 e	Day 1	Day 4	Day 11-14	Day 15	Day 25	Day 29	Day 39-42	Day 43	Day 46	Week 9	Week 10 onwards g	End of Study h
Informed Consent	Х														
Inclusion/Exclusion Criteria	Х														
Demographics and Medical History	Х														
Concomitant Medication Review	Х		Х		Х	Х		Х		Х				Xg	Х
Physical Examination		Х	Х			Х		Х		Х				Xg	Х
Vital Signs and Weight		Х	Х			Х		Х		Х				Xg	Х
ECOG Performance Status		Х	Х			Х		Х		Х				Xg	Х
Pregnancy Test – Urine or Serum β- HCG		X m													
PT/INR and aPTT		Х						Х							
CBC & Serum Chemistry a		Х	Xk			Х		Х		Х				Xg	Х
Urinalysis, T3, FT4 and TSH		Х								Х				Xf	Х
ECG		Xi		0				As c	linically	indicated	1				
Tumor Imaging - CT preferred b	Х												Xb		Х
Tissue Biopsy j	X			Х			Х		X		Х				
Correlative Blood Collection c		X						Х				Xc			Х
OBP-301 l,n				Х			Х		Х		Х				
Pembrolizumab Administration d, o					Х			Х				Х		X d	
Review Adverse Events					Х	Х		Х		Х		Х		Xg	Х

- a. Serum chemistry includes sodium, potassium, chloride, bicarbonate, blood urea nitrogen, creatinine, glucose, AST, ALT, Alk Phos, lactate dehydrogenase, bilirubin (total and direct), total protein, albumin, calcium, magnesium and phosphorous, may be drawn up to -2 days from schedule. b. Tumor imaging studies preferably CT scans of chest/abdomen/pelvis should be performed every three cycles of Pembrolizumab after week 10 until end of study.
- c. Correlative blood collection will be done at screening, day 25, day 46, at week 19 and at the end of study. Correlative blood draws will be done predose if treatment is given on the same day.
- d. Pembrolizumab will be administered every 3 weeks  $\pm$  3 days.
- e. Baseline assessment should be performed within 5 days of administrating first dose of OBP-301.
- f. Urinalysis, T3, FT4 and TSH should be performed every 3rd cycle of Pembrolizumab thereafter until end of study.
- g. From week 10 and onwards, concomitant medication review, physical exam, vitals/weight, ECOG performance status, CBC, comprehensive serum chemistry and review of adverse events should be performed every 3 weeks until end of study.

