- h. End of study will occur 28 days (+/- 5 days) following study removal, disease progression, or following 2 years on treatment. Patients may still be followed for survival for up to 96 weeks from study start.
- i 12-lead ECG will be recorded after the patient has rested for 5 minutes
- j. Tumor biopsy may be needed during screening phase for PD-L1 testing if there is no archival tissue available.
- k. Only needed, if screening CBC and chemistry done more than 7 days prior to first cycle of pembrolizumab.
- 1. OBP-301 will be administered every 2 weeks (-2 business day/+5 business day window). If the window is used, the following doses should be
- administered following the same window, ensuring at least 12 days between each OBP-301 administration.
- m. Pregnancy test for screening should be done within 7 days of Day 1.
- n. A CBC and CMP should be obtained within 10 days of OBP injection, if not already performed.
- o. OBP-301 and Pembrolizumab should not be administered on the same day.

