## 8 STATISTICAL ANALYSES

#### 8.1 General Considerations

Full details of the statistical analysis will be provided in a statistical analysis plan (SAP). Any changes to the planned statistical methods from the SAP will be documented in the clinical study report (CSR). The statistical evaluation will be performed using SAS®, version 9.4 or later.

All data will be presented in listings, ordered by patient, unless otherwise specified.

Descriptive statistics for continuous variables (number of patients [n], number of patients with missing data, mean, standard deviation, minimum and maximum) and categorical data (n, percent, number of patients with missing data, by category) will be presented.

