#### 8.3 Handling of Missing Values and of Values outside the Detection Limits

Missing values will not be imputed. All missing values will be reported in the listings as either "missing" or as the justification for the value being missing (e.g., "ND" [test not done] or "BQL" [below quantitation limit], where appropriate.

While efforts will be made to avoid incomplete or missing data, in rare cases the AE date could be incomplete or missing. If this happens, incomplete or missing dates will be imputed. For the calculation of AE duration and AE onset from dosing, missing AE dates will be imputed using a conservative approach. This approach will assume that the AE is treatment emergent where insufficient date information exists to determine if the AE occurred before or after dosing, except where year is missing. If the year is also missing then it will be assumed that the start is before the start of the study.

Imputed onset dates of AEs will be checked to ensure they occur after the first study day and before the resolution date. Imputed resolution dates will be checked to ensure they occur after the onset date and before date of last study visit (where AE is not flagged as ongoing).

Descriptive statistics for demographics, body weight, vital signs, and ECG data will be calculated from actual data only, with the number of actual data points used for the calculation of the summary statistics reported.

For censored safety lab data (i.e., hematology, clinical chemistry and urinalysis results that are outside the limit of quantification) the actual values reported by the laboratory (e.g., "< 2" for bilirubin) will be presented in the data listings. For the calculation of summary statistics, safety laboratory data values below the lower limit of quantification (LLOQ) will be set to  $\frac{1}{2}$  the LLOQ.

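### Section 8.7.4 plans shift tables for cytokines and immune-cell phenotypes without giving categories, and no change-from-baseline summary stands behind them

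*Combined protocol and SAP*

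**What the plan says.** Section 8.7.4 is a single sentence: "Summary statistics and shift tables will be presented for all special laboratories results including cytokines, and immune cell phenotypes by study visit".

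The rule for sorting laboratory values into low, normal and high is in section 8.7.3. Flags are "based on the investigational site laboratory normal range and/or the NCI toxicity criteria", and shifts run from baseline to every later visit. That section opens with chemistry, hematology, coagulation and urinalysis. Table 4 in section 6.5.5.1 lists the same four groups and contains no cytokine or immune-cell phenotype.

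Section 8.1 lists the summaries for continuous variables as the number of patients, "number of patients with missing data, mean, standard deviation, minimum and maximum". It also promises by-patient listings and defers full statistical detail to a SAP. Section 8.3 says "Missing values will not be imputed".

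Footnote c to the Schedule of Events says "Correlative blood collection will be done at screening, day 25, day 46, at week 19 and at the end of study". Footnote h says "End of study will occur 28 days (+/- 5 days) following study removal, disease progression, or following 2 years on treatment".

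**The concern.** For these markers the plan names one within-patient analysis, the shift table, and gives nothing from which to build its categories. A programmer could not produce the table from this text, or would have to choose cut-points after seeing the data.

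The other promised output is a set of visit means and SDs. These do not use each patient's own screening value. With no imputation, each visit describes whoever gave a sample, so a difference between two visit means mixes change within patients with change in who is present. Arithmetic means and SDs of raw cytokine values can also be dominated by one or two extreme results among about 37 patients.

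The protocol's own rationale is within-patient. Section 1.1 reports the phase I cytokine result as IL-6 and IL-10 rising in 8 of 9 and 7 of 9 patients. Visit means cannot yield such a count.

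**Working it through.** The documents state no figure for these markers, so there is none to reproduce. The check has three steps.

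**1. Is there a basis for the categories?** Section 8.7.4 promises shift tables. Section 8.7.3 supplies the only category rule (site range and/or NCI grade). Table 4 does not list the markers, and no range, cut-point or change category for them appears in the supplied text. Section 8.1 has no change score. The gap is therefore the missing categories together with the missing change summary.

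**2. Can a visit mean move when no patient changes?** Give each patient a constant log marker value with SD 1. Give each patient also a normally distributed tendency to leave, correlated ρ with that value. Keep the fraction q least inclined to leave. Then

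expected shift in the log mean = −ρ × φ(z_q) / q, where z_q is the standard normal quantile at q.

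With q = 0.5 the factor is 0.399 / 0.5 = 0.798. Both q and ρ are assumptions.

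| ρ | shift in log mean | ratio of geometric means | apparent fall |
|---|---|---|---|
| 0.2 | −0.16 | 0.85 | 15% |
| 0.3 | −0.24 | 0.79 | 21% |
| 0.5 | −0.40 | 0.67 | 33% |

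A simulation of 20,000 trials of 37 patients gave −0.161, −0.239 and −0.398. The paired change was zero in every case.

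A second run tied retention to figures in the Synopsis. It used the expected (60%) and historical (33%) disease control rates as stand-ins for the share still on study, which is again an assumption. Of 37 evaluable patients, 37 × 0.60 gives 22 and 37 × 0.33 gives 12. If leaving is unrelated to the marker, the chance SD of the apparent shift is √(1/m − 1/n), with m retained out of n:

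- m = 22: √(1/22 − 1/37) = 0.14 SD
- m = 12: √(1/12 − 1/37) = 0.24 SD

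With 100,000 simulated trials per setting and no change in any patient:

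| retained of 37 | ρ | mean size of shift (SD) | P(shift of at least 0.25 SD either way) |
|---|---|---|---|
| 22 | 0 | 0 | 7% |
| 22 | 0.3 | 0.19 | 33% |
| 22 | 0.5 | 0.32 | 71% |
| 12 | 0 | 0 | 29% |
| 12 | 0.3 | 0.33 | 63% |
| 12 | 0.5 | 0.54 | 91% |

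The direction depends on whether high or low values go with leaving. The paired change is again zero throughout.

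**3. What does pairing do for precision?** For the same m patients measured twice with within-patient correlation r, the variance of the difference in means is 2σ²(1 − r)/m when paired and 2σ²/m when treated as unpaired. The ratio of standard errors is √(1 − r): 0.71 at r = 0.5 and 0.55 at r = 0.7. Both values of r are assumptions.

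**Where it bites.** Days 25 and 46 precede the first on-treatment scan at Week 9, so little dropout for radiologic progression has occurred by then. Week 19 comes after that scan. The end-of-study draw is intended for patients who leave, so shrinkage is not its main problem. Its timing runs from soon after early progression to past 2 years, and a single visit mean mixes these times.

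**The case against.** A reader might infer that the plan contains no within-patient look at these markers and leaves only unpaired means. The documents do not support that. A shift table is itself paired, section 8.7.3 defines shifts from baseline, and by-patient listings will show each patient's screening and later values. The number of patients and the number missing are reported at each visit, so a shrinking set would be visible. Section 8.6 plans longitudinal profiling of tumor tissue and infiltrates, so 8.7.4 is not the trial's only view of immune change, although 8.6 names no paired statistic.

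It can also be said that the plan prints no normal range for any analyte, that 8.7.3 speaks of all laboratory values, and that cut-points are ordinary content for the SAP to which 8.1 defers. This stands as far as it goes: ranges may exist elsewhere. Nothing supplied shows that they do for research cytokines or cell phenotypes.

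Two further limits stand. No text says that the 8.7.4 assays are run on the blood described in footnote c, so that link is inferred. And 8.7.4 names no test, interval or between-visit contrast, so the standard-error ratio compares with an analysis a reader would do by eye, not one the plan specifies.

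The 15% to 33% also depends on the latent model. If 0.3 were instead the correlation with the yes/no fact of leaving, with half leaving, the shift would be 0.30 (ratio 0.74).

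**Conclusion.** The point holds as a gap in specification and a weak choice of summary. As written, 8.7.4 cannot produce its shift tables for these markers from the documents, and the continuous summaries that accompany them carry no change from baseline. That a visit mean can drift without any patient changing is certain. The size is not known: retention, log SD and ρ are all assumed, and nothing in the documents links baseline marker level to leaving. The 15% to 33% is an illustration and should not be read as a forecast. Nor should it be applied to every visit; the dropout argument bears mainly on Week 19.

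The output is descriptive and exploratory. It has no bearing on the response-rate decision, so this is a cheap improvement and not a threat to the trial's conclusion.

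**What to change.** In section 8.7.4, replace the shift tables for cytokines and immune-cell phenotypes with within-patient change from the screening sample. If categories are pre-specified, keep the shift tables and add the change summary. At each scheduled post-baseline draw at which the marker is assayed, in patients with both samples, report:

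- for cytokines, the geometric mean ratio to screening; for cell percentages, the mean or median difference;
- the 95% CI and the number of pairs;
- the screening values of those same patients alongside.

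Use median and quartiles for raw cytokine values. State which blood draws supply these assays, and show the spread of times behind the end-of-study row.

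The cost is wording and programming; if the assays use the draws already scheduled, no new samples are needed. Patients without a screening sample drop out of the paired tables. Pairing removes the effect of who remains on the baseline level, but the result still describes only patients who gave the later sample. Log ratios also need a rule for values below the quantification limit, because the half-LLOQ rule in section 8.3 is written for routine safety laboratory data.
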